## Abbreviations

Abbreviation	Full name
AA	Adverse event
AAG	Serious adverse event
CITY	Unexpected adverse event
API	Application programming interface
BPC	Good Clinical Practice
CDD	Direct data capture
CEIm	Drug Research Ethics Committee
CRD	Data Collection Notebook
CV	Cardiovascular/es
DD	Device deficiency
EAD	Adverse effect of the device
EAGD	Serious device adverse events
EAID	Unexpected adverse effect of the device
eCRD	Electronic Data Collection Notebook
EHFScB	European Heart Failure Self-care Behavior Scale
EIC	European Innovaton Council
EU	European Union
fevi	Left ventricular ejection fraction
HFmrEF	Heart failure with mid-range ejection fraction
HFpEF	Heart failure with preserved ejection fraction
HFrEF	Heart failure with reduced ejection fraction
IA	Artificial intelligence
IC	Heart failure
IT	Information technologies
LVAD	left ventricular assist device
MDPQ	Mobile Device Competency Questionnaire
NT-pro BNP	Propéptido natriurético cerebral N-terminal
NYHA	New York Heart Association class
PIC	Clinical Research Plan
PSSUQ	Post-Study System Usability Questionnaire
RRP	Patient-reported outcomes
SDK	Software development kit
THEIR	System Usability Scale

TM	Telemonitoring (Remote Monitoring)
UC	Usual care (Traditional follow-up)

## 2 Synopsis of clinical research

HumanITcare has implemented a cloud platform for telemonitoring of chronic patients through wearable medical devices and an alarm-based system that issues health alerts when a patient's biomedical

measurement is outside a predefined clinical range. The platform frees doctors and caregivers from reviewing each patient's data for anomalies, speeding up the decision-making process and reducing hospital visits. With the present study we aim to validate the effectiveness of the app for patients and digital platform for medical professionals by evaluating the increase in the quality of life of patients and measuring the reduction in the incidence of the main critical events of HF. Additionally, the study will validate the new API interoperability standards and platform architecture and evaluate the usability of the platform by delivering satisfaction questionnaires to patients and professionals at the end of the study.

This study is being carried out within the framework of a European project promoted by the European Innovation Council (EIC).

### Evidence to date

In 2020, a single-center study was carried out at the Torrevieja Hospital in which an early version of the digital platform was validated. (Sanchez et al., 2020). A total of 32 patients participated, 16 as the control group and 16 as the study group. The study group was monitored remotely using the HumanITcare digital platform and wearable devices (smart scale, blood pressure monitor, pulse oximeter and smart watch) for 3 months, while the control group continued normal clinical practice.

The results showed that patients monitored by the HumanITcare platform are less likely to return to the emergency department. Additionally, the study group showed a reduction in hospital readmissions and 92% of patients would recommend using the platform. Finally, 100% of clinical professionals agreed that the platform improves health care and services, saves time on visits and satisfies remote medical care, which is an easy-to-use and easy-to-use system. learn to use. In addition, professionals affirm that the way of interacting with the system is pleasant and that the platform fulfills all the expected tasks.

## 3 Product under investigation

HumanITcare is telemedicine software for monitoring patients who require continuous and remote monitoring of their health status. It is a platform that processes information that comes from questionnaires and/or different sensors interconnected to the patient's App and that is transmitted to a medical portal so that the health professional can make decisions for therapeutic or diagnostic purposes or set alarms when the parameters are above or below thresholds defined by the clinician himself.

HumanITcare has different functionalities related to this data:

- Tracking and monitoring of health data obtained through interconnected sensors:
- blood pressure monitor
- pulse oximeter (pulse and oxygen saturation)
- smartwatch (heart rate, physical activity and sleep)

- smart scale (weight)
- thermometer (temperature)
- glucometer (blood glucose)
- monitoring of self-reported responses through questionnaires (validated symptoms, quality of life, self-care questionnaires, etc.)
- annotation of data from the patient's medical history (necessary for correct monitoring, since alerts must be personalized to each condition)
- configuration of medical alerts (healthcare professionals can define several alerts per patient when certain parameters are above or below thresholds defined by the same clinician).

The platform intelligently monitors users in a fully automated manner, with real-time communication of their data, with special emphasis on passive data, thus demanding less attention from them.

The HumanITcare software offers the doctor the possibility of viewing all this monitored information in each user's profile to be able to interpret it more easily along with their history. This allows you to see:

- The evolution of chronic diseases
- Patient adherence to treatment
- The evolution of a patient after an intervention
- The need to make possible changes in medication or treatment due to a detected complication

All information about the product is found in the Researcher's Manual.

## 4 Rationale for clinical research design

### Evaluation of preclinical trial results

The preclinical tests in order to verify the effectiveness and safety of the HumanITcare software have been brought together in the validation and verification documents of the MDSW Test Plan and MDSW Test Report software, following the indications of the MDR Regulation 745/2017 and the EN 62304:2006 standard. /A1:2015. This standard establishes a series of activities to be carried out during the software development and maintenance process, necessary to generate quality, highly reliable and secure medical software. HumanITcare complies with all activities required by the standard to determine the risks resulting from the operation of the software. These activities are detailed in the Software Development Plan document.

### Clinical data evaluation

Heart failure (HF) is a prevalent and fatal clinical syndrome that affects the quality of life of millions of people worldwide. Between 17% and 45% of patients with HF die within the first year and the rest die within 5 years (Tripoliti et al., 2017). Furthermore, these patients have a high risk of rehospitalization, their associated healthcare costs are enormous, and the longer the life expectancy, the higher the prevalence of the disease. (McDonagh et al., 2021). Symptoms of IC commonly include shortness of

breath, excessive tiredness, and swelling of the legs that may worsen with decompensation. (Schiff et al., 2003), so traveling to medical centers represents a disadvantage for these people. Remote monitoring technologies provide a feasible solution that allows for earlier identification of decompensation and better adherence to lifestyle changes and medication (Brahmbhatt & Cowie, 2019). Although telemonitoring using smartphones shows potential to reduce both the frequency and duration of hospitalizations for HF (Koulaouzidis et al., 2016) cannot be associated with reduced mortality from any cause (Koehler et al., 2011). Therefore, there is a need to search for more effective and precise methodologies. In recent years, the use of portable devices (wearables) that allow daily monitoring of the patient's physiological data combined with Artificial Intelligence (AI) has shown enormous potential to predict diseases related to the cardiovascular system, their adverse events and the patient's health status (Lee et al., 2022), including patients with HF (Guidi et al., 2015).

HumanITcare is a platform that allows this remote monitoring through the integration of different medical devices and self-reported data. The platform allows you to customize a monitoring plan so that healthcare professionals can adapt this tool to the needs of a specific patient group or at the individual patient level.

The HumanITcare platform has been used in different therapeutic areas to improve personalized patient monitoring. Some of the areas in which an improvement in patient monitoring and health status has been demonstrated would be cardiology (IC - (Sanchez et al., 2020); cardiac rehabilitation - (Calvo-López et al., 2023), palliative care (Castillo Padrós et al., 2022), respiratory diseases, or oncology, among others.

## 5 Risks and benefits of the product in investigation, clinical procedure and clinical research

### **Benefits**

During the usual clinical practice of monitoring newly decompensated HF patients, the patient must monitor their vital signs daily and, if alarming values occur, communicate this by telephone or through a visit to the emergency room to the medical team in charge of their case. That's why the digital platform for medical professionals and the application for patients provides the following benefits:

1. Greater patient participation. The patient app can provide patients with the tools and resources needed to self-manage their condition and improve their understanding of treatment plans and lifestyle changes, leading to greater patient engagement and adherence.
2. Increased quality of life. With the app, patients can monitor their symptoms, vital signs and medications from their homes, which is very beneficial in patients who have mobility problems such as patients with insufficiency cardiac surgery.

3. Better outcomes for patients. Telemonitoring can help medical professionals identify early signs of deterioration in patients with HF and trigger timely interventions to prevent exacerbations, ultimately leading to improved clinical outcomes.
4. Digital health tools. Integrating telemonitoring with other remote monitoring technologies and digital health tools can provide a more complete view of a patient's health status and improve overall management of their condition in real time.

### **Adverse reactions**

The safety profile will be evaluated by recording, reporting and analyzing initial medical conditions, adverse events, physical examination findings, including vital signs and laboratory tests.

The notification of adverse events will be carried out as established by the latest guideline on Safety Notification in clinical investigations with medical devices for compliance with Regulation (EU) 2017/745 (MDCG 2020-10/1-*Safety reporting in clinical investigations of medical devices under the Regulation (EU) 2017/745*).

### **Associated risks**

The benefit/risk ratio for patients using HumanITcare is very high or high, since there are potentially no risks from the use of the product or the tests performed.

The manufacturer FollowHealth SL, Through risk management documents, establishes and commits to maintaining a continuous process during the life cycle of the product and its accessories to identify the hazards associated with a product, estimating and evaluating the associated risks, controlling these risks and monitoring the effectiveness of the controls.

This process follows the instructions of the EN ISO 14971:2019 standard and is carried out as follows:

- The risks are analyzed.
- The risks are evaluated.
- Actions are implemented to control risks.
- Residual risks are evaluated.
- The benefit versus risk is analyzed if there is an unacceptable residual risk after the implementation of the corrective actions.
- All product production and post-production information is collected to carry out a review of the risk management carried out.

The procedure for carrying out product risk management is explained in detail in the associated documentation that can be found in the risk management plan and associated procedures: Risk Management Plan.

The results of the analysis, including the identification of the main risks, their evaluation and the corrective measures to be applied, are collected in the Risk Management Matrix.

It should be noted that no residual risks associated with the use of HumanITcare have been described.

## 6 Objectives and hypotheses of clinical research

### 6.1 Main objectives

- To evaluate the effectiveness of telemonitoring to improve the quality of life of patients with HF.
- To study the impact of telemonitoring on patients' psychological well-being, including anxiety, depression, and sense of control over their condition.
- To evaluate the feasibility and acceptability of integrating telemonitoring technologies and digital health tools, and investigate their potential impact on patient outcomes as well as treatment adherence.
- Identify any adverse events or unintended consequences associated with telemonitoring of patients with heart failure, such as privacy issues or technical problems.

### 6.2 Secondary objectives

- To evaluate the role of telemonitoring in identifying early signs of deterioration in patients with heart failure and triggering timely interventions to prevent exacerbations.
- Improve clinical outcomes for patients with heart failure, as well as reduce hospital readmissions.

### 6.3 Hypothesis

The hypothesis of the study is that the implementation of a telemonitoring system in patients with heart failure will improve the quality of life and psychological well-being in patients, which will result in a decrease in symptoms of anxiety and depression, as well as a increased feeling of control over your state. Additionally, the incorporation of digital health and telemonitoring tools is expected to increase treatment adherence and improve patient clinical outcomes. On the other hand, telemonitoring is expected to be feasible and acceptable to patients, without generating significant adverse events or unwanted consequences. Ultimately, it is hypothesized that telemonitoring will allow early identification of signs of worsening in patients with heart failure, enabling timely implementation of therapeutic interventions to prevent exacerbations and optimize the clinical management of these patients.

## 7 Clinical research design

### 7.1 Generalities

#### 7.1.1 Study type

This is a multicenter, randomized (1:1) controlled trial.

#### 7.1.2 Duration of the investigation

Patients will be monitored for 3 months. The duration of the study has been defined based on the period of time in which recently decompensated HF patients are more likely to relapse and suffer harmful clinical events, and therefore to present a deterioration in their perception of quality of life.

#### 7.1.3 Variables

##### **Endpoint principal**

- Composite of quality of life, self-care and adherence to treatment by the patient (Change in the scale value of each questionnaire at 3 months)

The variables are quantified using validated scales. These measures are:

- Patient-Reported Self-Care Behavior Scale Measures (EHFScB Scale)
- Quality of life assessed through the "Minnesota Questionnaire for People with Heart Failure (MLHF questionnaire)"
- Patient adherence to treatment and medication intake (SMAQ Simplified Medication Adherence Questionnaire)

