##### **Secondary endpoints**

- Quality of life evaluated through the "Minnesota Questionnaire for People with Heart Failure" (Change in the value of the questionnaire scale at 3 months)
- Patient-Reported Self-Care Behavior Scale Measures (EHFScB Scale) (Change in Questionnaire Scale Value at 3 Months)
- Patient adherence to treatment and medication intake (SMAQ Simplified Medication Adherence Questionnaire) (Change in the value of the questionnaire scale at 3 months)
- Death from cardiovascular (CV) causes (Total number of patients who died in 3 months)

- Mortality from any cause (Total number of patients who died in 3 months)
- Acute HF decompensation (first and recurrent) during the follow-up period (Number of total decompensations in 3 months).

An acute decompensation of HF is defined as a new episode of symptoms and signs that requires intravenous decongestive treatment or increased oral diuretics either on an outpatient basis (e.g., day or home hospitalization for HF) or at home, emergency department or requiring an unplanned hospital admission.

- Hospital readmission due to HF decompensation (Total number of hospitalizations in 3 months)
- Hospital readmission for CV causes (Total number of hospitalizations in 3 months)
- Visits to the emergency room due to HF decompensation (Total number of visits to the emergency room in 3 months)
- Visits to the emergency room for CV causes (Total number of visits to the emergency room in 3 months)
- Medical care costs (Sum of costs for medication consumption, hospitalization, emergency care and medical transportation in 3 months)

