#### 7.1.4 Sample calculation

The sample calculation has been made based on the fact that a change of 5 points on the scale of the Minnesota Questionnaire for People with Heart Failure (MLHF questionnaire) between the control group and the experimental group (telemonitored) is clinically significant. (Rector, n.d.). Assuming an alpha risk = 0.05 and a beta error of 20%, we need to recruit a total of 253 participants divided into a control group and an experimental group.

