## 8 Design and statistical analysis

### 8.1 Methodology and analysis

Specific subgroup analyzes will be performed based on the different baseline data and risk factors available for the project. We will also test interactions between each pair of subgroups and the main effect of treatment.

Independent t tests or Mann-Whitney U tests will be used to compare the questionnaire scores based on the distribution of the data, whether normally distributed or not, respectively.

The incidence of secondary endpoint events in the two study groups will be described using Kaplan-Meier survival curves, which will be compared using the log-rank test. The hazard ratio will also be obtained using Cox proportional hazards regression models comparing the TM and UC groups. The time of each event will be calculated from the day of registration. We will compare the number of readmissions and days of hospitalization between the two groups using the Wilcoxon rank sum test.

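### The primary endpoint is called a composite of three questionnaires but has no score or success rule, and 253 is sized on one of them, so alpha 0.05 and 80% power are not established for it

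*Combined protocol and SAP*

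**What the plan says.** Section 7.1.3 gives the primary endpoint as "Composite of quality of life, self-care and adherence to treatment by the patient (Change in the scale value of each questionnaire at 3 months", and names EHFScB (self-care), MLHF (quality of life) and SMAQ (adherence) as its measures. The secondary list in the same section repeats all three 3-month changes, beginning with "Quality of life evaluated through the" Minnesota questionnaire.

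Section 7.1.4 rests the sample size on "a change of 5 points on the scale of the Minnesota Questionnaire for People with Heart Failure (MLHF questionnaire" scale between arms, with alpha 0.05 and beta 20%, and concludes that "we need to recruit a total of 253 participants divided into a control group and an experimental group". It mentions neither EHFScB, SMAQ nor a composite, and gives no SD, sidedness or dropout allowance.

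On analysis, section 8.1 says only that "Independent t tests or Mann-Whitney U tests will be used to compare the questionnaire scores", with the choice of test depending on the distribution.

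The first main objective in section 6.1 is "To evaluate the effectiveness of telemonitoring to improve the quality of life of patients with HF". The synopsis has a double aim: "evaluating the increase in the quality of life of patients and measuring the reduction in the incidence of the main critical events of HF". Section 6.3 adds that the intervention "is expected to increase treatment adherence and improve patient clinical outcomes".

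**The concern.** One combined score and three separate changes are different endpoints. The definition uses the language of both, and nothing elsewhere chooses between them. There are no weights, no standardization, no responder definition and no any-of or all-of rule. Table 1 appears to give SMAQ a 0 to 4 range against 0 to 100 for the other two scales (its columns may be broken in extraction), so raw changes could not simply be added. Followed literally, section 8.1 yields three unadjusted tests and no statement of what counts as a positive trial.

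What counts as success could therefore be settled after the results are known. According to section 16.2, those results feed the clinical evaluation for CE marking. The only error rate and power in the plan were derived for MLHF alone.

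**Working it through.** **Inputs from the plan.** Total 253, allocation 1:1 (126.5 per arm on average), MLHF difference 5, alpha 0.05, power 80%. **Not in the plan, so assumed:** two-sided testing, the SD, the losses, the correlation between scales, and the effects on EHFScB and SMAQ.

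**1. Can 253 be reproduced?** For two means, n per arm = 2·SD²·(1.960 + 0.842)²/5². Without an SD this has no answer, so I solve for the SD: SD = 5·√(n/2)/2.802.

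- No losses, n = 126.5: 5 × 7.953/2.802 = 14.19 (14.14 with the exact t calculation).
- 253 already allows for 10% losses, n = 113.9: 13.47 (exact 13.4).
- 253 already allows for 20% losses, n = 101.2: 12.70 (exact 12.6).
- One-sided, no losses: 15.99 (exact 15.95).

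Forward check, two-sided: SD 14 gives 248 in total and SD 14.2 gives 254. So 253 is an attainable figure for MLHF alone, but only with an SD that the plan does not state. At 253 with none missing, power is 91% if the SD is 12 and 51% if it is 20.

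Steps 2 to 4 take MLHF alone to have exactly 80% power, which is a standardized effect of 5/14.19 = 0.352.

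**2. Any one of three suffices, each at two-sided 0.05.** With independent scales the chance of at least one false significant result is 1 − 0.95³ = 14.3%. With equal correlation ρ, from three correlated normal statistics:

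| ρ | 0 | 0.5 | 0.7 | 0.8 |
|---|---|---|---|---|
| Error, either direction | 14.3% | 12.5% | 10.9% | 9.8% |

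Counting only false benefit, the first three are 7.3%, 6.3% and 5.5%, against 2.5% for a single test.

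**3. All three must succeed.** Type I error is controlled. If each scale has 80% power, joint power with independent scales is 0.8³ = 51%.

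| ρ | 0 | 0.5 | 0.7 | 0.8 |
|---|---|---|---|---|
| Joint power | 51% | 61% | 66% | 69% |

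Joint power can never exceed that of the weakest scale. If EHFScB and SMAQ each had 95%, it would be 72%, 76% and 78% at ρ = 0, 0.5 and 0.7.

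**4. Equal-weight mean of the three standardized changes.** This is one test at 0.05, so multiplicity does not arise. The variance of the mean is (3 + 6ρ)/9, which is 1/3 at ρ = 0 and 2/3 at ρ = 0.5. Power = Φ(effect/√variance × √63.25 − 1.960).

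- Only MLHF responds, effect 0.352/3 = 0.117: Φ(1.617 − 1.960) = 37% at ρ = 0; Φ(1.144 − 1.960) = 21% at ρ = 0.5.
- All three respond by 0.352: Φ(4.852 − 1.960) = 99.8% at ρ = 0; Φ(3.431 − 1.960) = 93% at ρ = 0.5.

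**The case against.** The best defence takes the word composite at face value. A single combined score needs one test at 0.05, and listing its components as secondary endpoints is ordinary practice. On that reading the repeat listing is no fault and alpha is not inflated. Both points stand. They do not supply the score, however, and step 4 shows that power under this reading runs from 21% to 99.8% depending on how the other two scales respond.

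The opposite defence is that the definition plainly means three co-primary endpoints. Even then the plan does not say whether one or all must succeed, and steps 2 and 3 show how far those differ.

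A reader might infer that the false-positive rate is in fact inflated. The documents do not support that: it follows only under an any-of-three rule, which they do not state.

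A reader might also infer that 253 is too few, or that missing questionnaires will leave the trial short. That is not supported either. Section 7.1.4 gives 253 as the number to recruit, so it may already allow for losses. Applying dropout to an SD that was back-solved with no dropout would be circular. Nor does 253 suffice only at an SD of about 14.1 with complete data: an SD of 12 with 20% missing gives 83.8% power, and 13 with 10% missing gives 82.4%.

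**Conclusion.** The point holds and should be fixed before any outcome data are seen. The primary endpoint has no combining or success rule, and the stated 0.05 and 80% belong to a single MLHF comparison. That conclusion needs no assumption, because it rests on reading 7.1.3, 7.1.4 and 8.1 together.

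The size does rest on assumptions: the rule eventually adopted, correlations from 0 to 0.8 (0 to 0.5 for the averaged score), and MLHF alone having 80% power. The conclusion is that alpha and power are not established for this endpoint. It is not that either fails, nor that 253 is wrong.

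**What to change.** **Preferred, in 7.1.3 and 8.1.** Name the between-group difference in 3-month MLHF change as the single primary endpoint at two-sided 0.05. It is the variable on which 253 was sized, and quality of life is the first main objective. Test EHFScB and SMAQ as key secondaries, either in a fixed order chosen by the sponsor or with Holm, and only after MLHF succeeds. Drop MLHF from the secondary list.

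**Alternative.** Keep the composite, but pre-specify either its score and single test or an all-three rule, and restate the power for that rule. The components may then stay as secondaries. To illustrate the cost: all three significant with 80% joint power needs 0.8^(1/3) = 92.8% per scale. If the scales are independent and each has effect 0.352, that is 2 × (1.960 + 1.463)²/0.352², or 189 per arm and 378 in total.

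**In 7.1.4.** State the SD, sidedness and dropout allowance behind 253.

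**Minor.** In section 7.4 the TM Day 0 and Day 90 lists omit SMAQ. The corresponding UC lists, the TM monthly schedule and Table 1 include it. Reconcile the wording.

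**Cost.** A protocol amendment, which under section 10 is likely to need ethics committee and agency review. Under the preferred option, claims on self-care and adherence become conditional on MLHF, but the change itself requires no extra patients. It does not settle the data-dependent choice between t and Mann-Whitney tests, or the handling of deaths and missing 3-month scores. Those still need their own text.
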